
40% less patient-controlled opioid analgesia use than controls during the 48-hour post-operative period, with lower pain ratings^{26, 27, 30}. This series of studies was the first to demonstrate the potential of brain stimulation technology to be part of a standard post-operative pain-management strategy, however TMS is more complicated to deliver than tDCS, has more adverse events, and is more cumbersome in the post-operative setting. In two independent preliminary pilot studies, the PI has shown that tDCS can reduce post-operative PCA use by as much as 46% while simultaneously reducing subjective pain ratings. Thus, a handful of preliminary studies have demonstrated the potential for brain stimulation techniques to adjunctively manage post-operative pain, but a more definitive trial is needed to evaluate the efficacy of tDCS using a more rigorous experimental design. Further more data is needed to determine optimal tDCS dosing parameters before tDCS will become a viable clinical intervention for post-operative pain across surgical specialties.

Aim-1: Determine the effects of transcranial direct current stimulation (tDCS) on post-operative pain, patient-controlled analgesia (PCA) use, and post-surgical complications during the 48-hour post-operative period following total knee arthroplasty (TKA) or total hip arthroplasty (THA).

Hypothesis 1: Real tDCS (over sensory/motor and dorsolateral prefrontal cortices) will be associated with decreased PCA morphine-equivalent usage (primary outcome), decreased pain ratings (secondary outcome), and decreased post-operative complications compared to sham tDCS.

Aim-2: Collect preliminary data regarding dose-dependent effects of tDCS on post-operative pain, PCA morphine-equivalent usage, and 6-month outcomes.

Hypothesis 2a: The analgesic benefits of tDCS will be dose dependent such that one 20-minute post-operative tDCS session will be superior to sham, two sessions will be superior to one session, and four sessions will produce the largest analgesic effects in the present study.

Hypothesis 2b: Patients receiving higher doses of real tDCS will evidence lower incidence (and dose) of 6-month opioid medication use, reduced pain, and better quality of life.

B. BACKGROUND AND SIGNIFICANCE

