tDCS Effects on Post-Procedural Pain Pilot:¹⁰² Recently, the PI conducted the first-ever pilot study on the effects of tDCS on post- Endoscopic Retrograde Cholangiopancreatography (ERCP) pain. Nineteen Caucasian females (mean age=37.2 StdErr=2.4) were enrolled. After ERCP, participants were randomly assigned to receive 20-minutes of tDCS with anode over the left-prefrontal cortex and cathode over the gut representation of the sensory cortex. No serious adverse events were associated with tDCS. Side-effects of tDCS were limited to tingling (42%), itching (47%) and mild stinging (11%) under the electrodes. Patients that received a single 20-minute dose of real tDCS used 22% less total hydromorphone than those that received sham at the end of the 24-hour inpatient post-procedural period (Cohen's $d=.38$). The slope of the cumulative PCA usage curve was significantly steeper in the sham tDCS group compared to real ($t(355)=10.80, p<.0001$). VAS pain scores suggested an arithmetic advantage for real tDCS compared to sham (not statistically significant likely due to limited power). *Results from this pilot feasibility study suggest that tDCS is safe, well-tolerated, and may be able to reduce post-ERCP opioid requirements without increasing subjective pain ratings.*

[figure not shown]
tDCS Effects on Post-Total-Knee-Arthroplasty (TKA) Pain Pilot: In a very recent preliminary pilot study, the PI randomly assigned 40 patients undergoing unilateral TKA to receive a total of 80 minutes of real ($n=20$) or sham tDCS ($n=20$) with the anode over the knee representation of the motor strip and cathode over the right dorsolateral prefrontal cortex. 20-minute tDCS treatments were delivered: 1) in the PACU, 2) 4 hours later, 3) the morning of post-operative day-1, and 4) the afternoon of post-operative day-1. VAS pain and mood ratings were collected every 4 hours following surgery provided that patients were awake. The slopes of the cumulative PCA usage curves were significantly different between groups, and those TKA in the real tDCS group used 44% less PCA dilaudid at 48-hours post-op ($p=.007$; Cohen's $d=1.0$). Despite significantly lower PCA dilaudid levels, VAS ratings of pain-on-average were also significantly lower in the real tDCS group ($t(37)=2.28, p=.029$). No adverse events or serious adverse events were encountered. There were no cases in which tDCS needed to be discontinued due to patient discomfort or tDCS-related complications.

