tDCS Electrode

Placement: All participants will have an EEG 10-20 cap placed F3 will be marked with a non-toxic felt-tipped pen. The tDCS anode will be placed over the mark (see figure 8) and the cathode will be placed over the right dorsolateral prefrontal cortex (F4). Electrodes will be held in place with Velcro straps.

tDCS Methods: tDCS will be delivered in four 20-minute-sessions (100 minutes total)

[figure not shown]
and will be conducted with the Phoresor-II Auto (Model PM850, Iomed, Salt Lake City Utah, USA) using 2mA current. This constant current device ramps up to the desired amplitude to minimize discomfort for participants and ramps the amplitude back to 0mA at the end of the programmed treatment duration. Electrodes will be standard small (4cm X 4cm) sponge electrodes soaked in a sterile solution of 0.9% sodium chloride insulated by a latex casing. The current density and total charge delivered by the above parameters is consistent with those used safely in the current research literature on tDCS. A very low dose (0.125mL) of topical benzocaine (6%) cream may be applied to the skin beneath the sponge electrodes for ~10 minutes and then removed if the participant experiences strong cutaneous sensations (patient report) during stimulation. After stimulation, a vitamin-E/Aloe cream will be applied to the skin under the electrodes following each treatment to reduce risks associated with skin drying.

tDCS Dosing: Custom-developed software will be used to generate random number sequences and save them in a file-format readable by the tDCS blinding software. Participants will be randomized to one of four groups in order to assess the effects of total tDCS charge on post-operative pain.

Group1 will receive a total of four 20-minute sessions of active 2mA tDCS (2 sessions on post-op day 0; and 2 sessions on post-op day 1)

Group2: will receive a total of two 20-minute sessions of active 2mA tDCS (2 sessions on post-op day 0; and 0 sessions on post-op day1) followed by 2 sessions of sham tDCS (both on post-op day 1).

Figure 8. Trajectory of anodal stimulation associated with the proposed tDCS electrode placement strategy

Group3: will receive a only one 20-minute session of active tDCS on post-op day 0, followed by three sessions of sham tDCS (1 on post-op day 0 and 3 on post-op day 1).

Group4: will receive a total of four 20-minute sessions of sham tDCS (2 sessions on post-op day 0; and 2 sessions on post-op day 1)

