Procedures and Flow: After determining eligibility and interest, written informed consent will be obtained from participants in the Orthopaedic Surgery Pre-operative clinic. Participants will complete the screening questionnaires and all questions about the study procedures, risks, and benefits will be answered. On the day of surgery, the corresponding Admission questionnaires will be completed. After surgery, participants will be transferred to the post-anesthesia care unit (PACU), awakened, and be hooked-up to standard clinical physiological monitors. Patients will be started on a PCA pump. Pain/mood ratings will be collected and the EEG 10-20 caps will be placed. The anode and cathode placement positions will be marked and the caps will be removed. Sponge electrodes will be soaked in saline, affixed in their rubber electrode casings, attached to the tDCS machine, placed on the scalp, and held in place with Velcro straps. The participant's study ID number and tDCS session number will be entered into the tDCS controller software, linked to the randomization file, and the stimulation session will begin (double-blind). After 20-minutes, the electrodes will be removed and pain/mood ratings will be collected again. Four hours later, the tDCS procedures will be repeated in the participants' hospital room. On post-op day-1, two tDCS sessions will be conducted separated by at least 3 hours. Pain and mood ratings will be collected before and after each tDCS session. Range of motion measurements will be collected before and after each physical therapy session. On the day of discharge, participants will complete the Discharge questionnaire packet. Total length of stay, and post-surgical complications will be recorded. At all follow-up time-points, participants will complete the corresponding measures and opioid use status will be tracked via patient report and verified via chart review.

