Statistical Analysis and Power: The orthopaedic surgeons at the Ralph H. Johnson VAMC conduct ~100 unilateral total knee arthroplasties and ~50 unilateral total hip arthroplasties each year . Thus, in order to meet the proposed n-size of the current study, 24 (out of 100) participants will need to be eligible and interested in participating in the trial each year. We will over recruit to permit for drop-outs and participants lost to follow-up. For analysis of primary outcomes associated with Aim-1, participants receiving any active tDCS (groups 1,2 & 3) will be collapsed and compared to the sham-only group. Multivariate multiple regression will be used with group-assignment entered into the model as a binary predictor. Surgery and anesthesia duration, depression & anxiety scores, sex, age, pre-tDCS pain, (ROM) Means and pre-op chronic opioid status will be entered into the model as covariates to permit for statistical control of these potentially confounding variables. Overall differences between real and

sham tDCS groups will then be examined for our primary outcomes: total post-op PCA morphine-equivalent dose, VAS pain-on-average ratings, and mean number of post-operative complications. Using the most conservative effect-size estimate from our series of pilot studies ($d=.70$), with 90 patients in the active tDCS group and 30 in the active-sham group, power is good to detect significant effects if they exist ($\alpha=.016$ (corrected for multiple DV's); $1-\beta >.80$; see figure 9). For Aim-2, MANCOVA will be conducted using all 4 groups and all primary dependent measures in the same model (controlling for surgery and anesthesia duration, depression & anxiety scores, pre-tDCS pain, physical rehab measures and chronic opioid status). With four groups of 30 patients each, assuming a moderate effect size $f^2(V)=.2$, and alpha of .05, power is good detect significant main effects in the model ($1-\beta >.80$). Secondary analyses will be conducted to evaluate long-term effects of tDCS on pain, functioning and quality of life (i.e., 2-wk, 4-wk, 8-wk, 3-month and 6 month-follow-up).

Problems/Challenges/Potential Pitfalls: The proposed tDCS device is an FDA-approved iontophoresis device, and its use for tDCS applications is off-label. The tDCS procedure is minimal-risk and FDA-

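### Aim 2 has no 4-session v 2-session contrast adjusted for opioid use before session 3, so that dose step would be read from a total that includes a period of identical treatment

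*Combined protocol and SAP*

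**What the plan says.** Section D, tDCS Dosing, gives Group 1 "four 20-minute sessions of active 2mA tDCS (2 sessions on post-op day 0; and 2 sessions on post-op day 1") and Group 2 "two 20-minute sessions of active 2mA tDCS (2 sessions on post-op day 0; and 0 sessions on post-op day1"), the latter followed by two sham sessions on day 1.

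Section D, Procedures and Flow, places session 1 in the PACU. For session 2 it says: "Four hours later, the tDCS procedures will be repeated in the participants' hospital room". For sessions 3 and 4 it says: "On post-op day-1, two tDCS sessions will be conducted separated by at least 3 hours". It gives no clock time for session 3. The nearest hint is the knee arthroplasty pilot in Section C, where that session was given on "3) the morning of post-operative day-1".

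Hypothesis 2a, in the aims that open the protocol, expects that "two sessions will be superior to one session, and four sessions will produce the largest analgesic effects in the present study".

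Under Statistical Analysis and Power in Section D, the primary outcomes are "total post-op PCA morphine-equivalent dose, VAS pain-on-average ratings, and mean number of post-operative complications". For Aim 2, "MANCOVA will be conducted using all 4 groups and all primary dependent measures in the same model". The plan states no pairwise or trend contrast between dose groups and no split of PCA use by session.

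**The concern.** Until session 3 starts, Groups 1 and 2 receive the same stimulation at the same times. Any difference between them in opioid use up to that point is chance. When that use is added into the total, the 4-v-2 comparison carries its variance without any treatment contrast to set against it.

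Dose dependence is a stated focus of the trial, and Section D says the findings will help decide whether a multi-site trial is needed. If the day-1 sessions do reduce opioid use, an imprecise comparison could easily be read as four sessions being no better than two. A simple source of precision, each patient's own use before the arms diverge, is not in the plan.

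**Working it through.** **The plan's own figure.** Aim 2 claims power above .80 for four groups of 30, f²(V) = .2 and alpha .05. With three outcomes, df1 = 3 × 3 = 9 and df2 = 3 × (120 − 4 − 3 + 3) = 348. Noncentral F power exceeds .999 with λ = f² × df2 or λ = f² × 3 × 120, and is .948 with λ = f² × 120. The claim is met on every convention, but it concerns the omnibus test and says nothing about 4 v 2. For a single pairwise test with 30 per arm at two-sided .05, 80% power needs d of about .74.

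**How long the arms are identical.** The documents give a 48-hour period (Aim 1) and PCA stopping on day 2 at an unstated hour. Assume PACU arrival between 10:00 and 16:00, session 3 between 08:00 and 12:00 on day 1, and either a 48-hour window or a PCA stop between 08:00 and 12:00 on day 2.
- Shortest share: 16:00 to 08:00 is 16 h, and 16/48 = 33%.
- Longest share: 10:00 to 12:00 next day is 26 h; with PCA stopped at 08:00 on day 2 the window is 46 h, and 26/46 = 57%.

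These are shares of time, not of dose. Groups 2 and 3 share only about the first 4 h: 4/48 = 8%.

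**Effect on precision.** Let E be use before session 3 and L use after it, with SD ratio k = SD(E)/SD(L), correlation r, and a 4-v-2 effect d in L only.
- Unadjusted total: d_total = d / √(1 + k² + 2rk)
- Late use alone: d
- Adjusted for E: d_adj = d / √(1 − r²)

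Assume d = .5 and r = .5, with 30 v 30 and a two-sided t test at .05:

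| Analysis | Effective d | Power |
|---|---|---|
| Total, k = .25 | .5/√1.3125 = .436 | .38 |
| Total, k = .5 | .5/√1.75 = .378 | .30 |
| Total, k = 1 | .5/√3 = .289 | .20 |
| Total, k = 1.5 | .5/√4.75 = .229 | .14 |
| Late use alone | .500 | .48 |
| Adjusted for E | .5/√.75 = .577 | .59 |

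With k = 1 and r from .3 to .7, the total has power .22 to .18 and the adjusted analysis .51 to .76. With d = .7, k = 1 and r = .5, the figures are .34 and .87. The adjusted analysis has the higher power in every case tried.

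**Total or late window?** Since total = E + L, regressing the total on group and E gives the same group coefficient, standard error and p-value as regressing L on group and E; only the coefficient on E changes, by 1. A simulated data set of 60 confirmed this. The gain therefore does not need a new outcome.

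**The case against.** **Whole-period use is the stated question.** The total estimates the opioid difference between regimens without bias, and total opioid spared is what a clinician would want to know. This stands. A reader might infer that the design hides the effect of the day-1 sessions. The documents do not support that: the expected difference in mg is unchanged and only its precision suffers. The total should stay, and adjustment does not change what it estimates for 4 v 2.

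**The size is assumed.** A reader might also infer that roughly 40% to 50% of the outcome carries no contrast. No passage says so. That range is a plausible share of time, but the outcome is dose. The ropivacaine blocks could lower early use and acute pain could raise it. The late-period d, the correlation and the SD ratio have no source in the documents either. This stands, so the powers above are illustrations.

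**The comparison favours adjustment.** Setting an unadjusted total beside an adjusted analysis mixes two changes; late use alone already reaches .48. The planned Aim 2 model also includes pre-tDCS pain, chronic opioid status, depression and anxiety scores and operative durations, which may absorb some of the same variance. This stands in part: the net gain over the planned model cannot be computed from the documents.

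**Aim 2 is preliminary and its test is omnibus.** Both are true. They argue for a secondary contrast rather than a new primary analysis. They do not supply an analysis of the 4-v-2 step that Hypothesis 2a names.

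**The pilot found d = 1.0 on the 48-hour total.** That pilot compared four active sessions with sham, arms that differ from session 1. It does not inform 4 v 2.

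**The data may not allow the split.** Table 1 lists PCA by day, and the day-1 column straddles session 3. The plan does not say that the pump download is time-stamped. Both clinical pilots in Section C analysed slopes of cumulative PCA use, which suggests that such data can be had but does not establish it.

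**Conclusion.** The point holds as a loss of precision in one dose step. It follows from the text alone that Groups 1 and 2 are identical until session 3, that the Aim 2 PCA measure is the undivided total, and that no 4-v-2 contrast is planned. How much is lost rests on assumptions: at a late-period d of .5 and correlation .5, power is .14 to .38 for the unadjusted total over SD ratios of 1.5 down to .25, against .59 with adjustment. The direction held at every value tried; the planned covariates may narrow the gap.

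It does not follow that the total is biased, that a known fraction of the dose is uninformative, or that the Aim 2 outcome must be redefined. The problem is also not of similar size for every dose step: Groups 2 and 3 diverge after about 4 h, and every active arm differs from sham from session 1.

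**What to change.** In Statistical Analysis and Power:
- Keep the four-group MANCOVA and the whole-stay total.
- Add one prespecified secondary contrast, Group 1 v Group 2 on PCA dose, with PCA use up to the start of session 3 as a covariate alongside the planned ones. State that this is equivalent to analysing use after session 3 with the same covariate.
- Handle VAS pain likewise: ratings after session 3, with earlier ratings as covariate. Ratings are already planned before and after each session.
- Restrict this covariate to the 4-v-2 contrast. In comparisons with Groups 3 and 4, use before session 3 is itself affected by treatment, so it should not enter the four-group model.
- The analogous 2-v-1 adjustment for use before session 2 is optional and would gain little.

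In the procedures, record the start time of each session, state when on day 1 session 3 is planned, and state that the pump log is time-stamped and will be split at session 3. Dependent Measures and Procedures and Flow also disagree on whether PCA starts after or before the first tDCS session; they must be reconciled so that the start of the total is defined.

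The cost is plan wording, recorded session times and one extra secondary contrast to report. No added patients are needed. The fix depends on a time-stamped download, which should be confirmed first.

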experience^{46 50}. Innocuous thermal stimulation is associated with activation of the anterior ACC whereas noxious stimulation is associated with activation of both the anterior ACC and the ventral portion of the posterior ACC⁵¹. Other brain structures that appear to be involved in the affective component of pain experience include the lateral and medial thalamus, insular cortex, and the supplementary motor area^{52 53}. There is some evidence supporting the notion that brain structures involved in processing the affective component of pain experience are activated bilaterally whereas structures involved in processing sensory-discriminative components demonstrate unilateral activation^{54 55}. The role of the left prefrontal cortex in pain control is unclear. However, there is evidence to support the concept that left prefrontal activation is negatively correlated with pain unpleasantness⁵⁶ suggesting a possible governing role of the prefrontal cortex on the affective dimension of pain experience. In fact, it has been shown that prefrontal activation is negatively correlated with pain catastrophizing⁵⁷. This is important as catastrophizing and pain-related anxiety have been identified as a reliable predictor of the development of chronic post-surgical pain.⁵⁸ Additionally, recent studies of expectancy and cognitively-mediated analgesia seem to suggest that cognitive effects on pain perception may involve genuine analgesia that is mediated by μ -opioid systems in the brain⁵⁹ and are associated with decreased activation of the thalamus, insula and anterior cingulate. These effects correlate with prefrontal cortex activation (where expectations, thoughts and belief-systems are believed to primarily operate in the brain⁶⁰). Thus, left prefrontal activation might result in similar analgesic effects, presumably by modulating limbic response to pain. Interestingly, there appears to be distinct laterality effects regarding dorsolateral prefrontal cortices. Activation of the left DLPFC but deactivation of the right DLPFC tends to be associated with pain inhibition (as well as improvements in mood).^{56, 57, 60}

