Stimulation of the primary motor cortex (M1) and dorsolateral prefrontal cortex (DLPFC) may both reduce the perception of pain, but they likely do so via different mechanisms. In a recent study, pain thresholds to electrical stimulation were assessed in 20 healthy volunteers before and during anodal tDCS. Four conditions of stimulation were compared: M1, DLPFC, occipital cortex, and sham. Anodal tDCS of M1 increased both detection and pain thresholds, while stimulation of DLPFC increased pain thresholds only. The results suggested that 1) anodal stimulation of M1 but not DLPFC could induce analgesia by modulating sensory discrimination and 2) stimulation of DLPFC could modulate the perception of pain via mechanisms independent of sensory perception¹⁹. An adjunctive study with 22 healthy volunteers showed that anodal tDCS of the DLPFC (but not M1, occipital, or sham) could decrease the perception of unpleasantness and reduces emotional discomfort/pain while subjects viewed emotionally aversive images²⁰.

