This dosing scheme will permit investigators to determine whether more stimulation over time is superior to less stimulation, as well as to determine the efficacy of motor tDCS in the management of perioperative pain.

Blind Maintenance: To ensure blinding, specially-developed software will be utilized to switch the tDCS on and off without any intervention from the patient or experimenters. This will be controlled via a silent solid-state relay driven by an Ontrak ADU218 (Ontario, Canada). For Sham tDCS sessions the stimulator will be turned off following 45s. The initial sham stimulation mimics the transient scalp sensation that is perceived when the stimulator is initially switched on. The order of treatment administration will be encoded in the software so that the administrator only enters a patient number and a session-number to start stimulation without knowing whether those specific numbers are associated with active or sham tDCS. The double-blind may only be broken if the clinical presentation of the patient suggests potential cognitive dysfunction, seizure activity, severe headache or extreme skin irritation under the electrodes.

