approval for tDCS applications using this device is not necessary. The PI has received MUSC IRB-approval for conducting tDCS in the perioperative setting and thus there are limited concerns about receiving approval to conduct the proposed research at the Ralph H. Johnson VAMC.

[figure not shown]
Competing Trials Locally or Nationally and Distinction:

The PI has an ongoing NIH-funded clinical trial of tDCS for post-operative pain at MUSC. However, that trial is focused on optimal cortical targets for stimulation (not dosing) and does not involve the veteran population. The proposed study will be on veterans and will focus on dose-dependent effects of tDCS on post-operative pain and post-surgical recovery.

Impact on Clinical Practice and Future Studies: If positive, this high-quality clinical trial could shift the paradigm of post-operative pain management to take advantage of recent neuroscience developments. Findings from this study will be used to evaluate the necessity for a multi-site clinical trial, and to develop future cross-surgical-specialty studies.

This study will be the first randomized, double-blind, controlled study of tDCS technology as an adjunctive pain management strategy for post-operative pain. Data from this trial will likely yield information regarding the feasibility and efficacy of tDCS as a post-operative pain-management approach. If the proposed pilot trial suggests significant and meaningful effects of tDCS as an adjunctive post-operative pain management strategy, this might change the way post-operative pain management is approached in the future. Findings from this study will be used to evaluate the necessity for an even larger-scale, multi-site clinical trial of the technique, and to determine whether future investigations of tDCS across different surgical specialties might be warranted.

Figure 9. Power by sample-size for primary aim of the proposed study (Aim-1 target n-size = 90 patients)

E. PROTECTION OF HUMAN SUBJECTS

E.1. Risks to subjects

Human Subjects Involvement and Characteristics

Subjects will be 120 patients undergoing TKA and THA surgery at the Ralph H. Johnson VAMC.

Inclusion/Exclusion Criteria

- 1) Between the ages of 25 and 90
- 2) No implanted medical devices above the waist
- 3) Mentally capable of reading, writing, giving consent, and following instructions
- 4) Not pregnant
- 5) Cleared for and scheduled for TKA or THA surgery
- 6) No history of seizures
- 7) Not allergic to latex rubber

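### The placement instruction gives every participant a bifrontal montage (F3/F4), but Hypothesis 1 and the close of the dosing section describe sensory/motor stimulation that no arm receives as written

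*Combined protocol and SAP*

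**What the plan says.** The only instruction on where the electrodes go is under tDCS Electrode Placement in section D. It reads "All participants will have an EEG 10-20 cap placed F3 will be marked", puts the anode on that mark, and adds that "the cathode will be placed over the right dorsolateral prefrontal cortex (F4"). The instruction covers every participant, and neither a motor nor a sensory site is marked.

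Two other statements describe something different. Hypothesis 1, under Aim-1, reads "Real tDCS (over sensory/motor and dorsolateral prefrontal cortices) will be associated with decreased PCA morphine-equivalent usage". The sentence that closes tDCS Dosing says that the scheme will show whether more stimulation is better than less, "as well as to determine the efficacy of motor tDCS in the management of perioperative pain".

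Procedures and Flow says only that the anode and cathode positions are marked. It names no site.

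**The concern.** The three statements cannot all be right. A patient treated exactly as the placement instruction says has no electrode over sensory or motor cortex, so the trial as written cannot show whether motor tDCS works.

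The protocol itself treats the distinction as substantive. Section B says that stimulation of primary motor cortex and of DLPFC "may both reduce the perception of pain, but they likely do so via different mechanisms".

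What is at stake depends on which text is wrong:

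- If F3/F4 is intended, a positive result could be reported as evidence for motor tDCS although no patient received it.
- If a motor anode is intended, staff who follow the instruction would stimulate the wrong site in every actively treated participant.

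**Working it through.** This is mainly a check of texts against each other. Arithmetic enters only to see whether the sample-size statement is affected.

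**Step 1. Sites, side by side.**

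| Place in the protocol | Anode | Cathode | Sensory/motor site? |
|---|---|---|---|
| D, tDCS Electrode Placement (this trial) | F3 | F4, right DLPFC | No |
| Hypothesis 1 (this trial) | not separated: sensory/motor and DLPFC | | Yes |
| D, end of tDCS Dosing (this trial) | called motor tDCS | | Yes |
| C, ERCP pilot | left prefrontal | sensory cortex (gut area) | Yes (cathode) |
| C, TKA pilot | motor strip (knee area) | right DLPFC | Yes (anode) |

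The placement instruction conflicts with two statements about this trial. Neither of the two post-procedural tDCS pilots used F3/F4. Each shares one electrode with it, at the same polarity: the ERCP anode and the TKA cathode.

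**Step 2. Does any arm supply the missing site?** No. The stated purpose of randomisation is dose: "Participants will be randomized to one of four groups in order to assess the effects of total tDCS charge on post-operative pain". The arms have 4, 2, 1 and 0 active sessions, that is 80, 40, 20 and 0 active minutes at 20 minutes each. They also differ in timing, since only Group 1 has active stimulation on post-operative day 1. All share one placement instruction. The question of targets is assigned to a different study: under Competing Trials the protocol says that "that trial is focused on optimal cortical targets for stimulation (not dosing) and does not involve the veteran population".

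**Step 3. Which text is more likely to be in error?**

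- *For F3/F4 being intended:* the instruction names both 10-20 positions. Pain and the Brain (section B) also gives a rationale for just such a pairing: "Activation of the left DLPFC but deactivation of the right DLPFC tends to be associated with pain inhibition".
- *Against certainty:* the placement sentence is garbled where the cap and F3 are mentioned. It also points to Figure 8, which is not shown in the text available here. The TKA pilot, the closest predecessor, used a motor anode that would fit Hypothesis 1.

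**Step 4. Power.** Inputs from Statistical Analysis and Power: d = .70, 90 active against 30 sham, alpha = .016. The plan does not state sidedness, so two-sided is assumed.

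- Noncentrality = d × √(n₁n₂/(n₁+n₂)) = .70 × √(90 × 30/120) = .70 × √22.5 = 3.32.
- Critical t on 118 degrees of freedom = 2.444.
- Power = 0.808 (noncentral t), or 0.819 by the normal approximation. The one-sided values are 0.874 and 0.880.

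The plan's figure of more than .80 reproduces. The montage does not enter this formula, so the arithmetic is the same under either reading.

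The support for d is a different matter. The plan draws d = .70 from the pilot series, and neither post-procedural tDCS pilot used F3/F4. For context only, the same two-sided calculation gives 0.99 at the TKA pilot's d = 1.0 and 0.26 at the ERCP pilot's d = .38. Neither value estimates the effect of F3/F4.

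**The case against.** The strongest reply is that this is leftover wording. Aim-1, the Overview and the analysis plan speak of tDCS without naming a site. The conflict comes down to a parenthesis in Hypothesis 1 and one adjective in the dosing section. Hypothesis 1 is also partly met, because it names DLPFC and the cathode is placed there. On this reading the protocol means F3/F4 and two phrases were not updated.

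Much of this stands. The visible text does lean that way, and Figure 8 may settle the matter. But Hypothesis 1 is where the tested intervention is defined, and the dosing sentence states what the trial will establish. Both still need to agree with what patients receive.

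A reader might infer more than the documents support:

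- *That the randomised comparison is compromised.* It is not. All groups share one montage, so real versus sham and dose versus dose remain valid comparisons of whatever is delivered.
- *That patients will certainly receive the wrong montage.* That follows only if the placement instruction is the error, which is the less supported reading.
- *That the trial needs an arm comparing sites.* Cortical targets are expressly left to another trial.
- *That power is wrong.* The stated figure reproduces. Only the evidence behind d = .70 is less direct than it appears.

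**Conclusion.** The inconsistency is real and should be fixed. As written, the trial can support conclusions about bifrontal (DLPFC) tDCS, not about motor or sensory/motor tDCS. The real-versus-sham comparison, the dose comparison and the power arithmetic at d = .70 (about 0.81) do not change. The two post-procedural pilots support the planning effect size only indirectly.

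This rests on three assumptions:

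- The placement text available here is complete apart from Figure 8.
- F3 is the left frontal counterpart of F4. The protocol labels only F4, and the rest follows from standard 10-20 naming.
- F3/F4 is the likelier intention. This is an inference, which is why confirmation comes first in the fix.

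Two slips in the same part of section D are separate clerical matters and carry no weight here: four 20-minute sessions make 80 minutes, not the printed 100, and Group 3's sham sessions by day do not add to its stated three.

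**What to change.** First, the sponsor should confirm the intended montage.

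**If F3/F4 is intended:**

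- Delete *sensory/motor* from Hypothesis 1 and *motor* from the sentence that closes tDCS Dosing.
- Repair the garbled placement sentence.
- Limit the trial's conclusion to bifrontal (DLPFC) tDCS.
- State in Statistical Analysis and Power that neither post-procedural tDCS pilot used this montage, so they support d = .70 only indirectly.

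The cost is wording only: no extra patients, visits or analyses.

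**If a motor anode was intended:** correct tDCS Electrode Placement before enrolment and give the site for both knee and hip patients. The TKA pilot's target was the knee area, and this trial also enrols hip arthroplasty. This changes the procedure, so its cost goes beyond wording. The sample-size arithmetic would still stand.
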